11. MEASUREMENT OF EFFECT

11.1 Antitumor Effect – Solid Tumors

For the purposes of this study, patients should be reevaluated for response every 8 weeks following completion of chemoradiation.

11.1.1 Definitions

Evaluable for Target Disease response. Only those participants who have measurable disease present at baseline, have received at least one cycle of therapy, and have had their disease re-evaluated will be considered evaluable for target disease response. These participants will have their response classified according to the definitions stated below. (Note: Participants who exhibit objective disease progression prior to the end of cycle 1 will also be considered evaluable.)

Evaluable Non-Target Disease Response. Participants who have lesions present at baseline that are evaluable but do not meet the definitions of measurable disease, have received at least one cycle of therapy, and have had their disease re-evaluated will be considered evaluable for non-target disease. The response assessment is based on the presence, absence, or unequivocal progression of the lesions.

11.1.2 Disease Parameters

Measurable disease. Measurable disease is defined as bidimensionally contrast enhancing lesions with clearly defined margins by CT or MRI scan, with two perpendicular diameters of at least 10 mm, visible on two or more axial slices that are preferably, at most, 5 mm apart with 0-mm skip. All tumor measurements must be recorded in millimeters (or decimal fractions of centimeters).

Non-measurable disease. All other lesions (or sites of disease), including small lesions (longest diameter <10 mm), are considered non-measurable disease. Bone lesions, leptomeningeal disease, ascites, pleural/pericardial effusions, lymphangitis cutis/pulmonitis, inflammatory breast disease, abdominal masses (not followed by CT or MRI), and cystic lesions are all considered non-measurable.

'Cystic lesions' thought to represent cystic metastases can be considered as measurable lesions, if they meet the definition of measurability described above. However, if noncystic lesions are present in the same participant, these are preferred for selection as target lesions.

11.1.3 Methods for Evaluation of Disease

All measurements should be taken and recorded in metric notation using a ruler, calipers, or a digital measurement tool. All baseline evaluations should be performed as closely as possible to the beginning of treatment and never more than 4 weeks before the beginning of the treatment.

The same method of assessment and the same technique should be used to characterize each identified and reported lesion at baseline and during follow-up.

11.1.4 Response Criteria

Response and progression will be evaluated in this study using the Response Assessment in Neuro-Oncology Criteria (RANO) and incorporating the updated iRANO criteria proposed specifically for brain tumors treated with immunotherapy as it allows for early inflammation- related changes and potential for delayed responses.

11.1.4.1 Evaluation of Target Lesions

Complete Response (CR): Complete disappearance of all enhancing tumor determined by two consecutive MRI scans not less than 4 weeks apart and no corticosteroid usage with a stable or improved neurologic examination for a minimum of 4 weeks.

Partial Response (PR): Greater than or equal to 50% reduction in tumor size of all measurable lesions on a stable or decreasing dose of corticosteroids, with a stable or improving neurologic examination for a minimum of 4 weeks.

Progressive Disease (PD): Progressive neurologic abnormalities not explained by causes unrelated to tumor progression (example: anti-epileptic drug or corticosteroid toxicity, electrolyte abnormalities, hyperglycemia, etc.) or a greater than 25% increase in the volume of the tumor by MRI scan. If neurologic status deteriorates on a stable or increasing dose of corticosteroids, or if new lesions appear on serial MRI scans, this will also be considered PD.

iRANO recommends confirmation of disease progression on follow-up imaging 3 months after initial radiographic progression if there is no new or substantially worsened neurological deficits that are not due to comorbid events or concurrent medication, and it is 6 months or less from starting immunotherapy. This includes if there is appearance of new lesions that could represent a transient inflammatory response. If progression is subsequently confirmed, the progression date should be the date the new lesion or concern for progression occurred.

Stable Disease (SD): A patient whose clinical status and MRI measurements do not meet the criteria for CR, PR or PD.

Unknown (UN): Assessment of target lesions cannot be made due to insufficient or unevaluable data. In this case, a concise explanation must be given.

Note: If tumor response data is missing for target lesions, the overall assessment must be UN unless there is new disease that would result in an overall assessment of PD. However, if there is missing or unevaluable data for non-target lesions, but data is available for all target lesions, the overall response for that time point will be assigned based on the sum LD of all target lesions. Additionally, the assessment of CR cannot be made if there is missing or unevaluable data for non-target lesions. In this case, the overall assessment would be PR.

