11.1.4.2 Evaluation of Non-Target Lesions

NA

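### Do the tumor-size rules in Section 11.1 conflict so that response and progression cannot be scored consistently?

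*Combined protocol and SAP*

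**What the plan says.** Section 11.1.2 defines measurable disease by two diameters at right angles, each 10 mm or more, and has all tumor measurements recorded in millimeters or decimal centimeters. Section 11.1.3 adds: "All measurements should be taken and recorded in metric notation using a ruler, calipers, or a digital measurement tool". It also says: "The same method of assessment and the same technique should be used to characterize each identified and reported lesion", at baseline and at follow-up.

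Section 11.1.4.1 then sets the size rules:

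- Progression includes, besides neurologic worsening and new lesions, "or a greater than 25% increase in the volume of the tumor by MRI scan".
- Partial response requires "Greater than or equal to 50% reduction in tumor size of all measurable lesions", with conditions on steroids and the neurologic examination.
- A note on missing non-target data says "the overall response for that time point will be assigned based on the sum LD of all target lesions". LD is not expanded and has no cut-off.

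The section headed "11.1.4.2 Evaluation of Non-Target Lesions" contains only a not-applicable entry.

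On which criteria apply, Section 11.1.1 says "These participants will have their response classified according to the definitions stated below". Section 11.1.4 opens with "Response and progression will be evaluated in this study using the Response Assessment in Neuro-Oncology Criteria (RANO"), and adds iRANO. Section 13.4 again names RANO with iRANO for radiographic response. Section 11.1.4.4 gives the smallest measurements since treatment start as the reference for progression. Section 11.1.7 has the treating physician determine response and provides for a later central review of all scans.

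**The concern.** Taken one sentence at a time, Section 11.1 seems to use three measures of size: volume for progression, an unspecified size for partial response, and a sum of LD in the note. The only size measurements it describes are lengths, and it does not say how a volume is obtained from them. Section 11.1.1 points to the written definitions, while Sections 11.1.4 and 13.4 point to RANO and iRANO. No sentence says which prevails if they differ.

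If that were a true conflict, the treating physician and the central team could both follow the protocol and class the same scan differently. Three results would be touched: the radiographic response proportion, progression-free survival (a secondary objective in Section 1.3), and the exploratory comparison of biomarkers between responders and non-responders in Section 13.4.

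**Working it through.** The plan gives no figure of its own on this point, so there is none to reproduce. The check reads the pointers together and then asks how far the possible readings of size differ.

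**1. The pointers.** The definitions to which Section 11.1.1 sends the reader include Section 11.1.4. That section opens by naming RANO and iRANO and then sets out the response categories. Section 13.4, which governs the analysis, names the same standard. The three places can be read as one chain. A ranking rule would matter only if the written categories differ from RANO. The documents do not reproduce RANO, so no difference can be shown from them.

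**2. Partial response.** Input: the 50% reduction in Section 11.1.4.1. Assumption: the lesion shrinks uniformly, so a product of two diameters scales as d² and a volume as d³.

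- By volume: 1 − 0.5^(1/3) = 0.206, a 20.6% fall in diameter. A 20 mm lesion must reach 15.9 mm.
- By product: 1 − 0.5^(1/2) = 0.293, a 29.3% fall. A 20 mm lesion must reach 14.1 mm.

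The readings disagree only between those limits. From 20 to 15 mm, the volume falls by 1 − 0.75³ = 57.8% and the product by 1 − 0.75² = 43.75%, so the call differs. From 20 to 12 mm, the falls are 1 − 0.6³ = 78.4% and 1 − 0.6² = 64%, so both readings give a partial response.

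**3. The longest-diameter reading.** If LD means longest diameter and size meant that, a 20 mm lesion would have to reach 10.0 mm, and the disputed range would be 10.0 to 15.9 mm. The only support for this reading is the missing-data note. That note applies when non-target data are missing, and non-target evaluation is not applicable. Measurability in Section 11.1.2 is two-dimensional. The sentence looks like text left over from a template and does not define partial response.

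**4. Progression.** The written measure is volume, with a threshold of 25%. Under uniform growth, 1.25^(1/3) − 1 = 0.077, which is 1.5 mm on a 20 mm lesion, whatever formula turns diameters into volume. The formula matters only for uneven growth. Suppose a 20 × 20 mm lesion grows in one diameter by a factor s. The threshold is reached as follows, depending on what the third axis is assumed to be:

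| Assumed third axis | Volume ratio | s for a ratio of 1.25 | Growth |
|---|---|---|---|
| Shorter diameter | s | 1.250 | +5.0 mm |
| Geometric mean | s^1.5 | 1.160 | +3.2 mm |
| Longer diameter | s² | 1.118 | +2.4 mm |

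None of these conventions is in the protocol. Section 11.1.3 allows a digital tool, which could measure volume directly and make the choice unnecessary.

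**5. Reach.** One patient reclassified moves a response proportion by 1/33 = 3.0 percentage points, using the evaluable number in Section 13.1. For comparison, the approximate 95% half-width is 1.96 × √(p(1 − p)/33). That is 10.2 points at an assumed p = 0.1 and 17.1 points at p = 0.5. The documents give no response rate and no basis for the number of patients who would fall in the disputed band.

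**The case for a change.** The strongest case for a change is that the cost is small and the ambiguity is real. Two competent readers can differ on a lesion that goes from 20 to 15 mm. The same-method rule in Section 11.1.3 holds a lesion to one technique over time, but it neither names the technique nor clearly binds the physician and the central team to the same one. No reference scan is given for partial response, and Section 11.1.7 does not say which read enters the analysis. A few sentences would settle all of this.

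The facts in that case stand: the volume calculation, the dimension for partial response and its reference scan are not written down. The inference that the plan must change does not follow. The remedy would leave the choice of measure to the sponsor and, if volume is kept, would only record how it is calculated. One central team reading every scan can already apply one measure to all patients, and the report can state which measure and which reads were used. The baseline scan described in Section 11.1.3 is the natural reference for shrinkage. The change is also not free of cost. Section 8.1.8 shows that patients have already been treated, so a measure fixed now that differs from the one in use could mean rescoring earlier scans.

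The iRANO confirmation step gives some protection. It asks for follow-up imaging 3 months after early radiographic progression without neurologic decline, so a marginal size crossing is not final. It does not remove the question, because confirmed progression is dated back to the scan on which it was initially suspected.

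**Conclusion.** No change to the plan is needed. Section 11.1 leaves out detail that readers can supply from a named standard, a same-method rule and a single central review team. The LD sentence is a clerical leftover with almost nothing to act on.

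The largest defensible effect is on partial response. If shrinkage is uniform and size means either volume or the product of two diameters, the call differs only when the diameter falls by between 20.6% and 29.3%. For progression, the written measure is volume, and the formula matters only when growth is uneven. Progression by new lesion or neurologic worsening does not depend on it.

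The results touched are descriptive or exploratory. Only patients with measurable disease at baseline can be evaluated for target response. Section 13.1 chose survival at 12 months as the primary endpoint to avoid the difficulty of measuring progression, and neither that endpoint nor its sample size uses tumor size.

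This conclusion rests on the uniform-shrinkage assumption for the partial-response band. It makes no claim about how the written categories compare with RANO, and takes no position on when treatment should stop for progression under Section 5.5.

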11.1.4.2 Evaluation of Non-Target Lesions

NA

11.1.4.3 Evaluation of New Lesions

The finding of a new lesion should be unequivocal (i.e. not due to difference in scanning technique, imaging modality, or findings thought to represent something other than tumor (for example, some 'new' bone lesions may be simply healing or flare of pre-existing lesions). However, a lesion identified on a follow-up scan in an anatomical location that was not scanned at baseline is considered new and will indicate PD. If a new lesion is equivocal (because of small size etc.), follow-up evaluation will clarify if it truly represents new disease and if PD is confirmed,

progression should be declared using the date of the initial scan on which the lesion was discovered.

11.1.4.4 Evaluation of Best Overall Response

The best overall response is the best response recorded from the start of the treatment until disease progression/recurrence (taking as reference for progressive disease the smallest measurements recorded since the treatment started).

11.1.5 Duration of Response

Duration of overall response: The duration of overall response is measured from the time measurement criteria are met for CR or PR (whichever is first recorded) until the first date that recurrent or progressive disease is objectively documented (taking as reference for progressive disease the smallest measurements recorded since the treatment started, or death due to any cause. Participants without events reported are censored at the last disease evaluation).

Duration of overall complete response: The duration of overall CR is measured from the time measurement criteria are first met for CR until the first date that progressive disease is objectively documented, or death due to any cause. Participants without events reported are censored at the last disease evaluation.

Duration of stable disease: Stable disease is measured from the start of the treatment until the criteria for progression are met, taking as reference the smallest measurements recorded since the treatment started, including the baseline measurements.

11.1.6 Progression-Free Survival

Overall Survival: Overall Survival (OS) is defined as the time from start of treatment to death due to any cause, or censored at date last known alive.

Progression-Free Survival: Progression-Free Survival (PFS) is defined as the time from start of treatment to the earlier of progression or death due to any cause. Participants alive without disease progression are censored at date of last disease evaluation.

Time to Progression: Time to Progression (TTP) is defined as the time from start of treatment to progression, or censored at date of last disease evaluation for those without progression reported.

11.1.7 Response Review

Response will be determined by the treating physician but all MRIs scans will be collected for later, central review of response by [name] and her team members.

12. DATA REPORTING / REGULATORY REQUIREMENTS

Adverse event lists, guidelines, and instructions for AE reporting can be found in Section 7.0 (Adverse Events: List and Reporting Requirements).

12.1 Data Reporting

12.1.1 Method

The Office of Data Quality (ODQ) will collect, manage, and perform quality checks on the data for this study.

12.1.2 Responsibility for Data Submission

Investigative sites within DF/HCC or DF/PCC are responsible for submitting data and/or data forms to the Office of Data Quality in accordance with DF/HCC SOPs.

12.2 Data Safety Monitoring

The DF/HCC Data and Safety Monitoring Committee (DSMC) will review and monitor toxicity and accrual data from this study. The committee is composed of clinical specialists with experience in oncology and who have no direct relationship with the study. Information that raises any questions about participant safety will be addressed with the Overall PI and study team.

The DSMC will review each protocol up to four times a year or more often if required to review toxicity and accrual data. Information to be provided to the committee may include: up-to-date participant accrual; current dose level information; DLT information; all grade 2 or higher unexpected adverse events that have been reported; summary of all deaths occurring with 30 days of intervention for Phase I or II protocols; for gene therapy protocols, summary of all deaths while being treated and during active follow-up; any response information; audit results, and a summary provided by the study team. Other information (e.g. scans, laboratory values) will be provided upon request.

Although an increase in toxicity is not anticipated with combination radiation, temozolomide, and bavituximab based on the mechanisms of action of these therapies and prior experience combining bavituximab with other cytotoxic chemotherapies, we will closely monitor patients for any unanticipated adverse events. Specifically, if 5 or more patients out of the first 20 treated and followed over a duration of 4 weeks are observed with CTCAE grade 4 or higher toxicity that is unexpected (i.e. not expected due to radiation, temozolomide, or bavituximab), then the treatment will be halted to determine if any changes need to be made to the design of the trial. This rule provides a one-sided 95% upper limit of 45.5%. Toxicities expected and related to temozolomide – specifically thrombocytopenia, leukopenia, lymphopenia, neutropenia, nausea or vomiting – will not be included in this early stopping rule since these are expected from temozolomide in rates as high as 46% of patients (Stupp 2005). Alopecia from radiation will also

not be included and neither will toxicities related to the underlying disease itself (ex. seizures). For any toxicity that may arise, the PI will review all unexpected CTCAE grade \geq 3 AEs to determine if any would warrant halting the trial. As stated above the DFHCC DSMB will also be monitoring this trial as an independent review.

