5. TREATMENT PLAN

5.1 Treatment Regimen

Bavituximab will be administered weekly for 18 weeks starting the first week of chemoradiation. Patients may continue beyond 18 weeks at the discretion of the treating physician if the patient is deriving clinical benefit. Cycle 1 will encompass the 6 weeks of chemoradiation. Cycles 2 onward will be 4 weeks in length. Treatment will be administered on an outpatient basis. Reported adverse events and potential risks are described in Section 7. No investigational or commercial agents or therapies other than those described below may be administered with the intent to treat the participant's malignancy with the exception of NovoTTF.

Cycle 1: Chemoradiation

	Reg	gimen Desc	ription		
Agent	Premedications; Precautions	Dose	Route	Schedule	Cycle Length
Bavituximab	Optional: Premedicate with 250 mg hydrocortisone IV and 50 mg diphenhydramine IV administered ideally 30 minutes prior to infusion	3 mg/kg	First IV infusion must be administered over approximately 90 (±10) minutes. If the first IV infusion is tolerated, subsequent infusions may be administered over 60 (±10) minutes	Weekly starting with the 5 th day of radiation (window = after 4 th dose but before 6 th dose). Administra tion can be at any time of the day that fits the patient's schedule regardless of RT or temozolom	Cycle 1 6 weeks

				ide administrat ion.
Temozolomide	Zofran 4-8 mg or	75mg/m2	PO	Daily for
	other anti-emetic as			up to 42
	needed			days

Cycle 2: Post Radiation

	Reg	gimen Desc	ription			
Agent	Premedications; Precautions	Dose	Route	Schedule	Cycle Length	
Bavituximab	Optional: Premedicate with 250 mg hydrocortisone IV and 50 mg diphenhydramine IV administered ideally 30 minutes prior to infusion	3 mg/kg	IV infusion can be administered over approximately 60 (±10) minutes if the first IV infusion was tolerated. Otherwise continue at approximately 90 (±10) minutes.	Weekly	4 weeks	

Cycle 3 onward: With Monthly Temozolomide

	Reg	gimen Desc	ription			
Agent	Premedications; Precautions	Dose	Route	Schedule	Cycle Length	
Bavituximab	Optional:	3 mg/kg	IV infusion can	Weekly		
	Premedicate with 250		be administered			
	mg hydrocortisone		over			
	IV and 50 mg		approximately		4 weeks	
	diphenhydramine IV		60 (±10)		4 weeks	
	administered ideally		minutes if the			
	30 minutes prior to		first IV infusion			
	infusion		was tolerated.			
			Otherwise			
			continue at			

			approximately 90 (±10) minutes.	

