10. STUDY CALENDAR

Baseline evaluations are to be conducted within 2 weeks prior to start of protocol therapy. Scans must be done \leq 2 weeks prior to the start of therapy. In the event that the participant's condition is deteriorating, laboratory evaluations should be repeated within 48 hours prior to initiation of the next cycle of therapy.

Assessments must be performed prior to administration of any study agent. Study assessments and agents should be administered within \pm 3 days of the protocol-specified date, unless otherwise noted.

	Pre-	Wk	Wk	Wk	Wk	Wk	Wk	Off Treatment ^e
	Study	1^{g}	2	3	4	5	6	On meannent
Bavituximab		Х	Х	Х	Х	х	Х	
Temozolomide		Х	Х	Х	Х	х	Х	
Radiation ^J		Х	Х	Х	Х	х	х	
Informed consent	Х							
Demographics	Х							
Medical history	Х							
Concurrent meds	Х	Х		Х			Х	
Physical exam ¹	Х	Х		Х			Х	Х
Vital signs ¹	Х	Х	Х	Х	Х	х	х	Х
Height	Х							
Weight ¹	Х	Х		Х			Х	
Performance status ¹	Х	Х		Х			Х	Х
Drug diary for temozolomide ^h		Х	X	Х	Х	X	Х	

Cycle 1: Radiation + temozolomide + bavituximab

CBC w/diff, plts	Х	X	Х	Х	Х	Х	Х	х
Serum chemistry ^a	Х			х				х
PT/INR/aPTT	Х							
ECG (as indicated)i	Х							
Adverse event evaluation		X		Х			х	Х
Tumor measurements via MRI ^b	Х							Х
B-HCG °	Х							
Tissue ^{d, k}	Х							
Correlative Blood Draws f	Х						Х	

b- MRI to be done at the Martinos Center for Biomedical Imaging

c – Serum Pregnancy Test (for women of childbearing potential)

d – Assessment to determine if there is sufficient tissue for correlative studies. Tissue may be sent as a batch later to minimize shipping requirements. Tissue is not required for registration.

e- This column included in case patient goes off study during cycle 1. This visit can occur within 2 weeks of the participant coming off study.

f – See section 9.2. Blood will be drawn prior to start of chemoradiation and during week 6 of chemoradiation.

g- First bavituximab infusion should happen after the 4th radiation treatment and before the 6^{th} treatment.

h- See Appendix B for the required drug diary.

i - if ECG is clinically indicated, the QTc-B rather than QTc-F should be used to look for abnormalities

J – Radiation dose not have to be done at a DFHCC site but should be considered to allow for ease of dosing bavituximab during radiation

K – MGMT status will be collected but is not required for registration

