13.5 Reporting and Exclusions

13.5.1 Evaluation of Toxicity

All participants will be monitored for 90 days from completion of radiation in order to assess for any AEs related to radiation and bavituximab regardless of duration of bavituximab.

Otherwise, all participants will be evaluable for toxicity from the time of their first treatment until 30 days after the last dose of bavituximab.

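### The only numeric toxicity trigger (section 12.2) has an unclear 4-week period: read as a counting window it closes before chemoradiation ends, and read as a minimum follow-up its exposure period is undefined

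*Combined protocol and SAP*

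**What the plan says.** Section 12.2 (Data Safety Monitoring) contains the plan's single toxicity rule with a count. It applies "if 5 or more patients out of the first 20 treated and followed over a duration of 4 weeks" show "CTCAE grade 4 or higher toxicity that is unexpected". Treatment is then halted while the design is reconsidered. Events expected from temozolomide, radiation alopecia and disease-related events are left out of the count. The plan adds: "This rule provides a one-sided 95% upper limit of 45.5"%.

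The regimen is longer than the rule's 4 weeks. Section 5.1 says "Bavituximab will be administered weekly for 18 weeks starting the first week of chemoradiation". It also says "Cycle 1 will encompass the 6 weeks of chemoradiation" and "Cycles 2 onward will be 4 weeks in length". Cycle 2 is bavituximab alone, and adjuvant temozolomide is added from cycle 3. Section 5.1 also allows bavituximab beyond 18 weeks at the treating physician's discretion. On the first dose, the section 10 calendar says "First bavituximab infusion should happen after the 4th radiation treatment" and before the 6th.

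Section 13.5.1 sets a longer period for toxicity in general: "all participants will be evaluable for toxicity from the time of their first treatment until 30 days after the last dose of bavituximab". It also monitors everyone for 90 days after radiation.

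Two further safeguards in section 12.2 have no numeric boundary. The principal investigator reviews every unexpected grade 3 or higher event and may halt the trial. The data and safety monitoring committee reviews the trial up to four times a year, or more often if needed.

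**The concern.** The rule is introduced as the specific check on unanticipated toxicity when bavituximab is added to radiation and temozolomide. Its 4-week period is not defined in two respects: when it starts, and whether it limits which events count or only sets how long the 20th patient must be followed before the count is made.

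On the first reading, qualifying events after week 4 fall outside the only numeric trigger, although they are collected under section 13.5.1. On the second, the first patients contribute far more exposure than the last, and the quoted confidence limit does not belong to any stated period. Either way, the committee cannot tell from the text what rate of delayed toxicity the rule is able to detect.

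**Working it through.** **1. The plan's own figure.** The exact one-sided 95% upper limit for 5 of 20 is the 0.95 quantile of Beta(6, 15) = 0.4556. This reproduces the stated 45.5% (truncated). The arithmetic is sound; what is missing is the period to which the rate refers.

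**2. Calendar** (day 1 = first radiotherapy day; cycle lengths from section 5.1).
- Planned regimen: 6 + 4 + 4 + 4 = 18 weeks. Four weeks is 4/18 = 22% of it.
- Window from radiotherapy day 1: ends on day 28.
- Window from first bavituximab dose (after the 4th and before the 6th fraction, so calendar days 4 to 8): ends between day 4 + 27 = 31 and day 8 + 27 = 35.
- End of the 6-week chemoradiation period: about day 42.
- Adjuvant temozolomide: 28 ± 7 days after radiotherapy (section 5.3.2), so day 42 + 21 = 63 at the earliest, 70 nominally, 77 at the latest.
- Smallest gap between a closed window and adjuvant temozolomide: 63 − 35 = 28 days.

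The choice of start date therefore does not change the result for a counting window.

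**3. Probability of triggering.** The documents give no event rate and no timing, so both are assumptions: 18-week rates *p* of 30% and 40%, with a 10% rate to gauge false alarms, and a constant hazard over 18 weeks. The trigger is X ≥ 5 among 20 patients.

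- *Counting window.* The 4-week rate is 1 − (1 − p)^(4/18): 1 − 0.70^(4/18) = 0.076 and 1 − 0.60^(4/18) = 0.107. X is binomial (20, 4-week rate).
- *Half of the affected patients have their event by week 4.* The 4-week rates are 0.15 and 0.20.
- *Minimum follow-up.* The count is made when the 20th patient reaches week 4. With evenly spaced accrual at 3 per month (section 13.2), patient i has follow-up f_i = min(18, 4 + (20 − i)/3 × 30.4375/7) weeks. Ten patients have the full 18 weeks, and 15 have passed week 10. Each patient's probability is 1 − (1 − p)^(f_i/18), and X is the sum of these unequal Bernoulli variables. The expected counts are 4.85 and 6.53.
- *Full 18-week count.* X is binomial (20, p).

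| Reading | p = 30% | p = 40% |
|---|---|---|
| 4-week counting window, constant hazard | 0.015 | 0.056 |
| 4-week window, half of events early | 0.17 | 0.37 |
| 4-week minimum, 3 patients per month | 0.56 | 0.84 |
| Full 18-week count | 0.76 | 0.95 |

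Accrual of 36 patients over 2 years, also in section 13.2, implies 36/24 = 1.5 per month. At that pace the minimum-follow-up figures are 0.66 and 0.90.

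**4. False alarms.** At an 18-week rate of 10%, the full 18-week count triggers with probability 0.043.

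**The case against.** A reader might infer that the rule never sees bavituximab with adjuvant temozolomide. The documents do not support so firm a statement. Section 12.2 does not say that events after week 4 are discarded. Four weeks can be read as the minimum follow-up of the 20th patient, and at 3 patients per month 15 of the 20 would then have passed week 10 when the count is made.

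A reader might also infer that later toxicity goes unmonitored. That is wrong. The investigator's review covers a lower grade, has no time limit and can halt the trial on a single event; committee review and serious adverse event reporting continue. The probabilities above are the chance that one rule fires, not the chance that the trial is halted.

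Three further points are fair. Nothing in the documents supports a constant hazard or a 30% to 40% rate of unexpected grade 4 or higher events. The triple combination exists only in cycle 1, and 4 weeks covers about two-thirds of that cycle, so a short early rule backed by judgement is a defensible choice. And waiting for 20 patients to complete 18 weeks before any look would be late: at 3 per month, about 10.5 months instead of 7.3, with about 32 instead of 22 of the 36 patients enrolled.

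These points limit the size and certainty of the concern. They do not remove the ambiguity, and nothing in the text explains why a numeric trigger thought necessary for the combination should stop before chemoradiation does. The timing objection is met by keeping the 4-week look.

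**Conclusion.** The point holds in a limited form. The only numeric trigger either stops counting at about day 28 to 35 of an 18-week regimen or counts over an unstated period that differs by patient. The two readings give very different rules: 0.015 against 0.56 at a 30% 18-week rate, and 0.056 against 0.84 at 40%. These figures rest on the assumed rates, a constant hazard and even accrual at 3 per month. If more events come early, the gap narrows; if all excess toxicity comes after week 4, a counting window cannot detect it. The calendar result rests on none of these assumptions. The stated 45.5% limit is correctly calculated but needs a period. This is an inexpensive improvement to safety monitoring, not evidence that patients lack oversight.

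**What to change.** Reconcile section 12.2 with section 13.5.1:

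- Keep the threshold, the event definition and the 4-week look for the first 20 patients.
- Continue the same count in those 20 patients over the planned 18-week regimen and the 30-day period already collected. Give the count this fixed end, because the section 13.5.1 period is open-ended for patients who continue bavituximab beyond 18 weeks.
- State when the period starts: first radiotherapy day or first bavituximab dose.
- State the period that the 45.5% limit describes, and give the rule's trigger probabilities over the period actually counted. The 18-week figures above leave out the extra 30 days, so they are a guide and not the properties of the revised rule.

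The cost is protocol wording. The adverse events are already collected. The rule stays open longer, and a temporary halt for review becomes slightly more likely (0.043 over 18 weeks if the true rate is 10%). No change to any patient's dose or management is proposed.
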